- Off-site IHCA team copilots will complete a brief questionnaire (attached). Most participants may complete the survey online using a version of this questionnaire implemented in REDCap.¹⁸ Opinions about the procedure will also be elicited through post-study qualitative interviews.
- ACLS protocol adherence and violations using a checklist adapted from previously validated research tools.^{8,40}
- Leadership behaviors will be evaluated according to a previously published taxonomy.¹⁹
- Overall function of the IHCA team will also be evaluated using a previously validated instrument.^{20,21}
- Number of simulation events and power analysis: Assuming a baseline no-flow percentage of 0.285,^{10,22} a best-case no-flow fraction of 0.08 (protocol guidelines advise a single 10 second pause in chest compressions for a pulse and cardiac rhythm check every two minutes), and equipment malfunction or simulation termination precluding event analysis for 15% of mock codes, we will require 76 completed mock codes (38 in each arm) to achieve 80% power to detect a 31% relative decrease (9% absolute decrease) in the mean no-flow fraction.
- Study duration: The 76 planned mock codes will be divided between the 7-8 participating institutions. We expect to complete 2-6 simulations at each participating hospital every 2 months. Accounting for scheduling conflicts and expected intermissions during implementation of a new electronic medical record at some study hospitals, we expect study completion to require 18-24 months (and potentially up to 48 months) after simulations begin.

Informed consent (“copilot” physicians): Members of the research team will approach the eligible subjects by email (see attached) or in person at their workplace. Interested subjects will be consented by research team member(s) according to the Intermountain Healthcare Informed Consent Policy.

Table 1: Descriptive & outcome measures for randomized trial of telemedical intensivist IHCA team copilot

Variable	Data source	
	Primary	Secondary
Response team characteristics		
Response team structure	In-person observation	Video recording
Past experience of code team members	Questionnaire	
Primary outcome		
Fraction of pulseless time with no chest compressions*	Simulator mannequin	
Secondary outcomes		
Time from onset of shockable rhythm to defibrillation	Simulator mannequin	Defibrillator
Fraction of chest compressions in target depth range^{23*}	Simulator mannequin	Defibrillator

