Fraction of chest compressions with incomplete release*	Simulator mannequin	Defibrillator
Fraction of 30s segments with 8-12 breaths/minute^{23*}	Simulator mannequin	Defibrillator
Fraction chest compressions at target rate (100-120/minute)*	Simulator mannequin	Defibrillator
Time to first dose of epinephrine	In-person observation	Video recording
ACLS protocol adherence fraction (using validated instrument)	In-person observation	Video recording

ACLS protocol errors of commission, timing and omission ²⁴	In-person observation	Video recording
Team Emergency Assessment Measure (TEAM) score ²⁰	In-person observation	Video recording
Number and types of input by telemedical intensivist copilot	Video recording	In-person observation
On-site provider experience during mock-code	Questionnaire	
On-site provider satisfaction with telemedical intensivist copilot	Questionnaire	
On-site provider short-form State-Trait Anxiety Inventory score ^{16,17}	Questionnaire	
Off-site copilot experience during mock code	Questionnaire	Qualitative interview
Audiovisual connection or equipment problems (logistic or technical)	In-person observation	Questionnaire

* Outcome measured over (1) primary analysis window and from (2) activation of telemedicine cart; (3) "Code Blue" activation; and (4) from arrival of first resuscitation team member until simulation termination

Data analysis:

The primary analysis will include completed simulation where CPR quality data is complete and non-corrupted. Simulations for which equipment malfunction preclude measurement of compression quality will be excluded from analysis. Simulation events where malfunction of audiovisual recording equipment or major deviations during simulation implementation prevent accurate evaluation of resuscitation team performance and protocol will be excluded from analyses addressing these topics. Prematurely terminated simulation events and simulation events classified as run-in events will be excluded from all analyses.

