Between-group comparisons for continuous variables will employ two-sided t-tests with unequal variance. Comparisons for binary or categorical variables will employ Fisher's exact test or chi-squared test as appropriate. Given clustering within simulations, between-group comparisons of survey responses will employ multilevel logistic (for binary variables) or linear (for continuous variables) regression with a random effect for simulation event. Comparisons of Likert-style variables will use the rank-sum method described Datta/Satten.²⁸

Sample size/power analysis: Assuming a baseline no-flow percentage of 0.285, a best-case no-flow fraction of 0.08 (protocol guidelines advise a single 10 second pause in chest compressions for a pulse and cardiac rhythm check every two minutes), and equipment malfunction or simulation termination precluding event analysis for 15% of mock codes, we will require 76 mock codes (38 in each arm) to achieve 80% power to detect a 31% relative decrease (9% absolute decrease) in the mean no-flow fraction. We therefore expect to enroll 1900 on-site IHCA team members as study subjects (although some participants may participate in >1 mock code).

Waiver of Informed Consent and HIPAA Authorization (for on-site IHCA team members):

We are requesting a waiver of informed consent and HIPAA authorization for on-site IHCA team study participants of this study. Participation in this study is similar to standard training for IHCA team members and involves no more than minimal risk to the subject. Individuals will be notified by means of a prominently displayed poster(s) that a simulation-based research project with video recording is in progress. Such notification will address individuals reasonable expectation of privacy. We will not use video recordings for any purposes except research, and digital video recordings will be stored securely and then transferred to a secure, approved server of the Intermountain network. We will not systematically collect individually identifiable information. The research therefore involves no more than minimal risk to the subjects; the only potential risk is a breach of confidentiality, and protections are in place to safeguard the data. Because risk is minimal, the waiver of consent and authorization will not adversely affect the rights or welfare of subjects.

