The research could not practicably be carried out without the waiver of consent and authorization. Most hospitals have dozens or even hundreds of staff eligible to participate formally in IHCA responses. We would estimate that more than 2000 individuals are eligible for study participation. Team membership is also flexible, and the list of eligible IHCA team members for each hospital is expected to vary significantly over the 24 months of this study as staffing changes. Finally, for hospitals announcing IHCA team activations via a public address system, additional ad hoc participation by other staff is to be expected. For all of these reasons, we are unable to identify and consent in advance individuals who will participate in simulations. Moreover, including on IHCA simulation teams only those subjects for whom advance consent could be obtained would compromise the scientific validity of the study and preclude useful conclusions, as a large proportion of the data would be eliminated if obtaining consent were a requirement. Informed consent would markedly increase the response burden for participants, thereby reducing response rates and compromising study validity.

Similarly, obtaining consent after IHCA team activation and individual's arrival to the simulation site but prior to an individual beginning participation in the simulation is also not feasible. This would preclude the necessarily rapid formation of a IHCA response team and abolish the simulation's fidelity to actual cardiac arrest event, introducing significant bias into the results and compromising the scientific validity of the data obtained.

On-site participants in code simulations will be provided an information sheet about study participation at the time the simulation concludes.

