Data Collection: A research coordinator will be present at all mock codes. Besides study implementation duties, the coordinator will record team composition and function, processes of care, and leadership behaviors. Additional data will be obtained from (1) the simulator device, (2) the defibrillator device, (3) review of video recording of simulation event, (4) a brief questionnaire completed by IHCA team members upon completion of the mock code, and (5) a brief questionnaire completed by the telemedical physician copilot.

Data elements for collection

- Telemedical critical care physician (“copilot”)
 - Name
 - DOB
 - Email
 - Telephone
 - Race/ethnicity
 - Year completed medical school
 - Year completed post-graduate training
 - Date of first experience with telecritical care
 - Telecritical care shifts per year
 - Sex
 - Age
 - Credential type (MD vs DO)
 - Experience with in-person cardiac arrest events led
 - Date/time of each study simulation participation
 - Opinions about impact, utility, and feasibility of “copilot” interaction (survey)
 - Opinions about impact, utility, and feasibility of “copilot” interaction (post-participation qualitative interview)
- On-site code team participants
 - Event ID
 - Profession
 - Specialty (if physician)
 - Role on IHCA team
 - IHCA team participation frequency
 - Experience participating in mock code
 - Opinions about code team function during mock code
 - Opinions about impact, utility, and feasibility of “copilot” interaction
 - Short form State-Trait Anxiety Inventory^{16,17}
- Simulation events (see also Table 1)
 - Location
 - Date/time of event
 - Participant numbers and professions
 - Simulation duration
 - Date/time of key response parameters (i.e. team leader arrival)
 - Date/time of key resuscitation events
 - CPR quality
 - Interventions by IHCA team
 - ACLS protocol adherence
 - ACLS protocol deviation & errors

- Etiology identification
- IHCA team function
- Debriefing (Y/N) and themes
- Telemedicine interface function
- Leadership behaviors by IHCA team leader

Privacy, Confidentiality and Data Management

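### The multilevel models for on-site survey outcomes omit profession and code-team frequency, which are already collected; adding them would give a modest precision gain and partial protection against a differing respondent mix

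*Combined protocol and SAP*

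**What the plan says.** Data analysis states that "survey responses will employ multilevel logistic (for binary variables) or linear (for continuous variables) regression with a random effect for simulation event". For ordinal items it says: "Comparisons of Likert-style variables will use the rank-sum method described Datta/Satten". Neither sentence names a respondent characteristic.

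Under Data elements for collection, the list for on-site code team participants includes profession, specialty for physicians, role on the team and "IHCA team participation frequency". The list for simulation events includes "Participant numbers and professions". Table 1 places "Past experience of code team members" among the response team characteristics, with no stated use in the analysis. Its secondary outcomes include on-site provider experience and "On-site provider short-form State-Trait Anxiety Inventory score".

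Respondents are a mixed group. Research subjects covers both designated team members and voluntary responders, 15 to 25 per event on average. The section on waiver of consent adds that, where activations go over a public address system, "additional ad hoc participation by other staff is to be expected". The questionnaire is anonymous and is completed after the simulation ends. Only some participants complete the anxiety scale, and no selection rule is given.

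**The concern.** Anxiety and perceived team function plausibly differ between, say, a nurse who attends codes often, a resident and an ad hoc attender. If they do, profession and past frequency explain part of the variation in responses, and a model without them leaves that part in the standard error of the arm contrast. Provider experience is one of the four effects named in the Study summary, so the precision of these comparisons has some value.

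There is also a secondary point about bias. Events are randomized, but who is still present and answers is settled after exposure to the assigned arm. If the mix of respondents came to differ by arm, an unadjusted comparison would attribute the resulting difference in scores to the copilot.

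**Working it through.** **Plan's own figure.** There is none to reproduce: the power statement covers the no-flow fraction only, and no survey variance, event-level correlation or response rate is given. The variance components below are assumptions.

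**Inputs.**
- Events per arm k = 32: 76 × 0.85 = 64.6, rounded down to 64 and split equally. The percentage cuts do not depend on k.
- Responses per event m = 20: the midpoint of 15 to 25, taking everyone as answering (assumed).
- Total response variance 1, event variance 0.05, variance explained by profession and frequency 0.20, so the residual is 0.75 (all assumed).

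**Formula.** Let f be the share of the covariate-explained variance that lies between events. Ignoring the small cost of estimating the covariate effects:
- Unadjusted: Var = (2/k) × [0.05 + 0.20f + (0.75 + 0.20(1 − f))/m]
- Adjusted: Var = (2/k) × [0.05 + 0.75/m]

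**Adjusted.** 0.05 + 0.0375 = 0.0875; SE = √(0.0625 × 0.0875) = 0.074.

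**Stable mix (f = 0).** 0.05 + 0.95/20 = 0.0975; SE = 0.078. Variance cut = (0.0975 − 0.0875)/0.0975 = 10%; the SE falls by about 5%.

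**Strongly varying mix (f = 0.11).** With four equally common professions, this means each one's share varies between events with SD √(0.11 × 0.25 × 0.75) = 0.14, or 14 points. Then 0.05 + 0.022 + 0.928/20 = 0.1184; SE = 0.086. Variance cut = (0.1184 − 0.0875)/0.1184 = 26%; the SE falls by about 14%.

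**Milder variation (SD 7.5 points).** f = 0.075²/0.1875 = 0.03. Then 0.05 + 0.006 + 0.944/20 = 0.1032, and the variance cut is 15%.

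**Other strengths of covariate, stable mix.** With 10% explained, the adjusted bracket is 0.05 + 0.85/20 = 0.0925, a 5% cut. With 30% explained it is 0.0825, a 15% cut.

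**Wider grid, stable mix.** With k = 38, m from 5 to 25, event variance 0.01 to 0.20 and covariates explaining 5% to 20% of within-event variance, the SE falls by between 0.3% and 10%.

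**Bias, if the measured mix differed by arm.** Bias = (arm difference in the share of experienced respondents) × (outcome gap between experienced and other respondents). The standard error, for k = 38, m = 20 and event variance 0.05, is √(2/38 × 0.0975) = 0.072 SD. The rejection rates come from 4,000 simulated trials per row with no copilot effect; the gaps and differences are assumed.

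| Arm difference | Gap | Bias, unadjusted | False-positive rate, unadjusted | False-positive rate, adjusted |
|---|---|---|---|---|
| 10 points, measured trait | 0.5 SD | 0.05 SD | 11% | 5% |
| 20 points, measured trait | 0.5 SD | 0.10 SD | 27% | 5% |
| 10 points, unmeasured trait | 0.5 SD | 0.05 SD | about 11% | about 11% |

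The last row shows the limit of the remedy: selection on something not in the model passes straight through, with or without adjustment.

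**The case against.** The strongest reply is that an analysis allowing for clustering, without covariates, is a legitimate comparison of randomized events. That stands. Chance variation in respondent mix between events is event-level variance, which the planned random effect already carries into the standard error. The planned inference is therefore valid, only less precise than it could be.

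A reader might infer that arm-related selection is actually present, for example that the copilot sends surplus staff away. The documents do not support this. The copilot's tasks under Methods/Procedures concern compressions, defibrillation, situational awareness, etiology and leadership; dismissing staff is not listed. The link or control video starts only once the team lead arrives or five minutes pass, so those who arrive earlier cannot have been selected by what the arm delivers. Nothing states or implies different response by arm. What remains is that the documents plan no check of it.

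A reader might also infer that even a small shift would matter. With a 0.5 SD gap, a 5-point shift gives 0.025 SD, about a third of a standard error (0.025/0.072). To reach about 0.074 SD, close to one standard error, the gap would have to be 0.074/0.05, about 1.5 SD, and nothing in the documents supports that.

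Two further limits stand. Who stays and answers is at root a non-response question, which covariates address only for the measured part. And Likert items stay unadjusted; how many of the experience items are Likert cannot be told from the documents.

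**Conclusion.** The point holds as an improvement, not as an error. For continuous and binary on-site survey outcomes (including the anxiety score, taken as continuous), the plan leaves out characteristics fixed before the event that it already collects. Under the stated assumptions the cost is a variance about 10% higher than it need be relative to the planned analysis if the mix is stable, rising to about 26% if each profession's share varies between events with an SD of about 14 points. The documents describe a varied, partly voluntary attendance but give no figure for its variation, so the upper end should not be taken as the expected value.

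Protection against bias is conditional and partial: it applies only if respondents differ by arm in profession or frequency, and only to that part. The primary outcome comes from the mannequin and is not touched.

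**What to change.** In Data analysis, state that the multilevel linear and logistic models for on-site survey outcomes, including the anxiety score, contain fixed effects for profession (with physician specialty grouped) and past participation frequency, alongside the planned event effect. Give blank items a missing category. State that a role taken up after cart activation is not adjusted for, since it may be a consequence of the arm.

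Add one descriptive table, by arm: survey response rate and respondents' profession mix, set against the recorded "Participant numbers and professions", with the same for the subset completing the anxiety scale. This checks for selection by profession using data already recorded. Participation frequency has no such denominator, because it is known only for those who answer.

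The cost is a sentence or two and a table, with no new data. The model loses a few degrees of freedom, and odds ratios from the logistic models become conditional on the covariates, which should be said when they are reported. Likert items remain on the planned clustered rank-sum test, unadjusted.

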teams or act as voluntary responders to announced mock codes will be eligible to participate. The number of on-site participants for each simulated IHCA event is expected to average 15-25.

- Telemedical intensivist IHCA copilot: Board-certified or board-eligible critical care medicine physicians on the staff of the Intermountain Healthcare Telecritical Care Center will act as IHCA team copilot. The total number of expected participants is up to 30.

Recruitment:

- Local IHCA team: IHCA team activation will employ the participating hospital's standard mechanism. A sign posted outside the room used for the mock code will indicate that a video-recorded simulation is taking place. After completion of the simulation, participants will receive an information sheet about the study.
- Telemedical intensivist IHCA copilot: Eligible telemedical intensivists will be invited to participate by email and in person.

Methods/Procedures:

- Study design: Randomized, multicenter, simulation-based clinical trial
- Intervention: Standardized consultation to IHCA team by off-site intensivist via two-way audiovisual link using a mobile telemedicine cart
- Control: Display of silent, pre-recorded, non-interactive videotape of an ICU physician. The on-site participants will be told that an intensive care physician is observing the mock code.
- Randomization: Each event will be randomly assigned to intervention or control using block randomization by hospital.
- Procedures:
 - All event will be randomly pre-assigned to intervention (participation via telemedicine link by a remote critical care physician) or control (prerecorded video of telemedicine physician displayed on mobile telemedicine cart).
 - A research coordinator will arrange a time for mock code with local hospital clinical leadership and Code Blue leadership. The remainder of the IHCA team will not be informed that the announced event is a simulation prior to team activation.
 - The research coordinator and an experienced simulation technician will set up simulation equipment in an unused patient care room on the general medical or surgical ward at the hospital, including video recording device and mobile telemedicine cart.
 - Research coordinator will obtain final confirmation with the on duty clinical leadership that simulation will not interfere with patient care.
 - The hospital's on duty IHCA resuscitation team will then be activated via the hospital's standard mechanism.

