 - Upon arrival to the room, members of the designated IHCA team and other care providers will be informed via a posted sign that the event is a videorecorded research simulation. They will then begin participate in the simulation at their discretion.
 - We will adapt existing, tested cardiac arrest simulation scenarios for use in this study. While the provided case histories will describe patients of different ages, genders, and presenting complaints, all scenarios will feature cardiac rhythms demanding substantively identical resuscitative actions (Figure 1).
 - The telemedical link (or a control video) will be activated by the research coordinator after the arrival of the team lead or after five minutes have elapsed, whichever occurs first. At this time, the coordinator will also provide simple, brief, and scripted "just-in-

time” training to the mobile telemedicine cart and, for intervention events, the telemedical intensivist copilot.

- For mock codes randomized to intervention, critical care physicians with experience in telecritical care who consent to participate in this study will provide standardized consultation to the on-site team. These IHCA team “copilots” will advice and assistance to the on-site team leader including help with ensuring high-quality, minimally-interrupted chest compressions and prompt defibrillation, assisting situational awareness, encouraging etiologic evaluation, and promoting leadership behaviors.
- The event will be terminated when team performs an action that was pre-determined for the scenario to result in return of spontaneous circulation. The simulation will be terminated no later than 25 minutes after initiation if team fails to perform this pre-determined action. Most simulations are expected to last 10-12 minutes.
- After simulation termination, participants will complete a brief, anonymous questionnaire.
- Local code team leadership and/or the on-site code team leader will lead a debrief of the event. As needed, the research coordinator or simulation specialist will facilitate discussion of the simulation.
- In progress mock code simulations may be terminated by on-duty hospital clinical leadership or physician code team members if clinical care of patients requires.

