- Mock codes terminated in progress due to competing clinical priorities prior to simulated return of spontaneous circulation will be excluded from the final analysis. If this occurs, the simulation event may be rescheduled at the same hospital for a later date, with the rescheduled mock code assigned to the same study arm as the aborted mock code.
- If systematic problems interfering with study implementation, data collection, or interpretation are identified after study initiation, the study may be halted temporarily while the systematic issues are addressed. Affected events where data is invalid will be considered part of a roll-in phase of the study and will be excluded from data analysis. For each assigned to roll-in event status, we will schedule a make-up event at the affected hospital. Make-up events will be assigned to the same study arm as the roll-in event being replaced and will be interposed randomly with other events at the affected study site.
- Data collection: A research coordinator will be present at all mock codes. Besides study implementation duties, the coordinator will record team composition and function, processes of care, and leadership behaviors. Additional data will be obtained from (1) the simulator device, (2) the defibrillator device, (3) videotaped recording obtained via the mobile telemedicine carts, and (4) a brief questionnaire completed by IHCA team members upon completion of the mock code.
- The primary outcome for the study will be the fraction of time between activation of the telemedicine cart and beginning of the pulse check following the subsequent second full cycle of CPR that the IHCA team does not deliver chest compressions (“no-flow fraction”). Secondary outcomes are shown in Table 1.
 - On-site IHCA team members will complete a brief questionnaire (attached) to measure the subjective experience of individual and team function and — when applicable,

[figure not shown]

Figure 1. Unified structure for mock code scenarios. (ROSC: return of spontaneous circulation.)

opinions about the simulated mock code. Some on-site study participants will also complete a short-form version of the State-Trait Anxiety Index (STAI)¹⁶ validated for measurement of state anxiety (i.e. anxiety/stress at the time the questions are answered).¹⁷ Some participants may complete the survey online using REDCap, a secure web application for building and managing online surveys and databases.¹⁸

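### The primary t-test leaves unused a recorded, plausibly prognostic factor: whether the team leader had arrived before the five-minute cart trigger

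*Combined protocol and SAP*

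**What the plan says.** Under Methods/Procedures (Procedures), the coordinator activates the live link or the control video "after the arrival of the team lead or after five minutes have elapsed, whichever occurs first". The rule is the same in both arms. The same section (Data collection) defines the primary outcome as the share without compressions of the "fraction of time between activation of the telemedicine cart and beginning of the pulse check following the subsequent second full cycle of CPR". Cart activation is therefore the start of the primary window.

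On allocation: "Each event will be randomly assigned to intervention or control using block randomization by hospital". Leader status plays no part in it.

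On analysis (Data analysis section): "Between-group comparisons for continuous variables will employ two-sided t-tests with unequal variance". No covariate or stratum is named. Regression is planned only for survey responses, because of clustering within events.

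The Data Collection list for simulation events includes "Date/time of key response parameters (i.e. team leader arrival", so the information needed to classify each start is already to be collected.

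Background and Significance says that effective leadership counters obstacles to good resuscitation and that leadership training improves care. It gives no figure for no-flow fraction by leader presence.

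**The concern.** The five-minute limb of the rule only operates when no leader has yet come, so the design allows two kinds of start: leader already present, or leader late. On the sponsor's own rationale the two could differ in no-flow fraction. Part of the copilot's described role is also "advice and assistance to the on-site team leader", so what the copilot does early in the window could differ too.

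Whether the leader arrived before the trigger is settled before the team sees either display, so adjusting for it does not condition on anything the intervention caused. An unadjusted comparison leaves any variation between start types in the error term. It also leaves the estimated arm difference exposed to a chance excess of late-leader starts in one arm. Both matter more in a trial of 76 events than in a large one.

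**Working it through.** **Inputs from the documents.** Control mean: "Assuming a baseline no-flow percentage of 0.285". Size and target: "we will require 76 completed mock codes (38 in each arm) to achieve 80% power to detect a 31% relative decrease (9% absolute decrease". Expected loss: 15% of events. Test: two-sided.

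**Not in the documents, so assumed.** Alpha 0.05. SD back-solved below. Share of late-leader starts q. Difference in mean no-flow between start types g. All power figures use the normal approximation.

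**Step 1: the plan's own figure.** The 76 cannot be reproduced independently without an SD and alpha, but it is internally feasible.
- Effect: 0.31 × 0.285 = 0.088, which rounds to the stated 0.09.
- Analysable events: 38 × 0.85 = 32.3 per arm; in reverse, 32/0.85 = 37.6, rounded up to 38.
- Implied SD = δ / [(1.960 + 0.842) × √(2/n)]. With n = 32, √(2/32) = 0.25, so 0.09/(2.802 × 0.25) = 0.1285. With δ = 0.08835 it is 0.1261.
- The power paragraph in Methods/Procedures calls the 76 events completed; the Sample size/power analysis section does not. If all 38 per arm are analysable, SD = 0.09/(2.802 × 0.2294) = 0.140.

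**Step 2: what adjustment would gain.** Variance explained: R² = q(1−q)g²/SD². Adjusted SD = SD × √(1−R²). Power = Φ(δ/(adjusted SD × √(2/n)) − 1.960).

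Worked case, q = 0.3 and g = 0.10: R² = 0.21 × 0.01/0.0165 = 0.127. Adjusted SD = 0.1285 × √0.873 = 0.1200. Then 0.09/(0.1200 × 0.25) = 3.00, and Φ(1.04) = 0.851.

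At 32 per arm, SD 0.1285, unadjusted power 80.0%:

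| q | g | R² | Power after adjustment |
|---|---|---|---|
| 0.1 | 0.05 | 1.4% | 80.5% |
| 0.2 | 0.05 | 2.4% | 81.0% |
| 0.2 | 0.10 | 9.7% | 83.8% |
| 0.3 | 0.10 | 12.7% | 85.1% |
| 0.5 | 0.15 (extreme) | 34.1% | 93.2% |

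With 38 per arm and SD 0.140, the first and fourth rows become about 80.5% and 84.3%.

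**Step 3: chance imbalance.** The SD of the between-arm difference in the late-leader share is √(2q(1−q)/n).
- q = 0.3: √(2 × 0.3 × 0.7/32) = 0.115. An imbalance of 1.96 SD with g = 0.10 shifts the arm difference by 1.96 × 0.115 × 0.10 = 0.022, a quarter of the 0.09 target.
- q = 0.1, g = 0.05: √(2 × 0.1 × 0.9/32) = 0.075, and the shift is 1.96 × 0.075 × 0.05 = 0.007.

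**Step 4: numbers by start type.** For q of 0.1 to 0.3, late-leader events number 0.1 × 32 = 3.2 to 0.3 × 32 = 9.6, or about 3 to 10 per arm.

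**The case against.** The strongest reply is that nothing is broken. The activation rule is identical in both arms and events are randomized, so the Welch test is unbiased and its standard error already allows for chance imbalance. An excess of three late-leader events in one arm, with g = 0.10, moves the difference by 3/32 × 0.10 = 0.009, about 0.3 of a standard error (0.1285 × 0.25 = 0.032). The SD was back-solved for an unadjusted comparison, so the 80% already absorbs this variation. All of this stands. A reader might infer that the unadjusted test is biased or that the trial falls short of its stated power; the documents support neither.

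A reader might also take leader absence to be an established cause of higher no-flow. The Background is qualitative and partly concerns leadership training. No passage says how often leaders will be late, or by how much no-flow would differ. The factor is plausible, not known.

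Finally, a reader might infer that the pooled result misses the research question, or that the copilot has nobody to help in a late-leader start. The research question, hypothesis and intervention are framed around the team, and the copilot's tasks include compression quality, defibrillation and situational awareness. The window covers two full CPR cycles, at least about four minutes with checks every two minutes, so a leader may well arrive within it.

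Two practical objections also hold. The documents do not say when the five minutes begin, so the indicator needs that definition first. And hospital, the blocking factor, has at least as good a claim to adjustment. Both are met in the fix.

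**Conclusion.** The point holds as a small, nearly free improvement. A factor that is already collected, fixed before exposure and plausibly prognostic is not used in the primary analysis. The cost of leaving it out is precision and protection against chance imbalance, not validity.

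The gain is from 80% to about 80.5% to 85% power, on these assumptions: 32 analysable events per arm, two-sided 5%, SD about 0.126 to 0.129, a late-leader share of 0.1 to 0.3 and a no-flow difference of 0.05 to 0.10. The 93% case should carry no weight: it needs half of events to start without a leader and a difference of 0.15, larger than the target treatment effect. If leader arrival hardly matters, or leaders are almost never late, the gain is close to zero and so is the cost of the term.

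One caveat is that the coordinator both activates the cart and observes the event, and the documents do not say whether that person is blind to arm. This is why the term should come from leader arrival time and not from actual activation time.

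**What to change.** In the Data analysis section, before results are seen:

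- Make the primary analysis a linear model of no-flow fraction on arm, a yes/no term for leader arrival before the five-minute trigger, and hospital, with heteroscedasticity-robust standard errors.
- State when the five minutes begin, and derive the yes/no term from recorded leader arrival on that same clock.
- Set a rule for dropping the term if almost no events start without a leader, based on the count over both arms combined and not on outcome data.
- Keep the planned Welch t-test as a sensitivity analysis.
- Report any results by start type as descriptive only. With about 3 to 10 late-leader events per arm, they should not be presented as separating support of a leader from replacement of one.

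The cost is a few sentences of text, one degree of freedom for the leader term, and one for each hospital after the first (6 to 7 with the 7 to 8 hospitals in the study-duration paragraph, 8 with the nine sites on the title page). No new data and no change to conduct are needed. Prespecification matters because the same adjustment added after unblinded results would look data-driven.
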